PROTOCOL SYNOPSIS

Study Title	NAD⁺ Precursor Supplementation with Exercise Training to Increase Aerobic Capacity in Freidreich's Ataxia
Funder	National Institutes of Health (NIH)
Clinical Phase	Mechanistic clinical trial (Phase II)
Study Rationale	Decreased aerobic capacity (VO ₂ max on exercise testing) is common in FA, and may contribute to decreased insulin sensitivity (S _i). Decreased muscle mitochondrial oxidative phosphorylation (OXPHOS) capacity is a potential cause of decreased VO ₂ max in FA. Preclinical and clinical studies suggest that exercise training and NAD ⁺ precursor supplementation may each produce increases in OXPHOS that translate into increased VO ₂ max. Also, the effects of exercise and NAD ⁺ precursor supplementation may be additive.
Study Objective(s)	
Primary
 
 To measure the effect of a combination intervention (NR + exercise) on VO₂max in FA. 
Secondary
 
 To measure the effect of combination administration (NR + exercise) on S_i in FA.
Supplement	
Tru Niagen ® Nicotinamide Riboside (NR) (300 mg capsules)
 
Placebo for NR

Study Design	
Randomized, placebo-controlled trial with a 2x2 factorial design testing the effects of an NAD⁺ precursor (NR) and exercise on VO₂max and S_i health in FA.
 
Participants will be assigned to 1 of 4 groups:
 
 - NR Supplement, Plus Exercise - NR Supplement, NO Exercise - Placebo for NR Supplement, Plus Exercise - Placebo for NR Supplement, NO Exercise 
The 12-week in-home intervention will include recumbent cycling, an activity with demonstrated safety, feasibility, and appeal in this cohort.¹¹

Subject Population	Inclusion Criteria
key criteria for Inclusion and Exclusion:	
 1) Molecular diagnosis of Friedrich's Ataxia (FA). 2) Males and Females, Age 10 to 40 years (inclusive). 3) Girls ≥ 11 years of age must have a negative urine/serum pregnancy test and must use an acceptable method of contraception, including abstinence, a barrier method (diaphragm or condom), Depo-Provera, or an oral contraceptive, for the duration of the study. 4) Not currently meeting exercise guidelines as outlined by The Physical Activity Guidelines for Americans. 
 - Children and Adolescents should do 60 minutes (1 hour) or more of moderate-to-vigorous physical activity daily. - As a part of their physical activity, children and adolescents should include muscle-strengthening physical activity on at least 3 days a week. - Adults should do at least 150 minutes (2 hours and 30 minutes) to 300 minutes (5 hours) a week of moderate-intensity, or 75 minutes (1 hour and 15 minutes) to 150 minutes (2 hours and 30 minutes) a week of vigorous-intensity aerobic physical activity. - Adults should also do muscle-strengthening activities of moderate or greater intensity that involve all major muscle groups on 2 or more days a week. 5) Cardiac echocardiogram or cardiac MRI, performed within 1 year of enrollment, showing a LVEF $\geq 45\%$ 6) ECG, performed within 1 year of enrollment, without clinically significant arrhythmia. 7) Weight > 24 kg 8) Parental/guardian permission (informed consent) and if appropriate, child assent.
	Exclusion Criteria
	
 1) Known sensitivity to NR. 2) Concurrent use of any medications, including statins, likely to increase risk of NR toxicity. 3) HgbA1c $\geq 8.5\%$ and/or DM requiring insulin or insulin secretagogue.

-
- 4) Use of supraphysiologic steroids
 - 5) Laboratory abnormalities that indicate clinically significant anemia or bleeding risk.
 $\text{Hgb} < 10 \text{ g/dL}$ or $\text{Platelets} < 100\text{K}$
 - 6) Laboratory abnormalities that indicate clinically significant kidney disease using serum creatinine and MDRD equation.
 $\text{eGFR} < 60 \text{ ml/min/1.73 m}^2$
 - 7) Laboratory abnormalities that indicate clinically significant liver disease.
 $\text{AST/SGOT} \geq 3.0 \times \text{ULN}$
 $\text{ALT/SGPT} \geq 3.0 \times \text{ULN}$
 - 8) Uncontrolled and persistent arrhythmias that are felt to be clinically significant
 - 9) Known history of moderate or severe left ventricular systolic dysfunction ($\text{LVEF} < 45\%$)
 - 10) Standard contraindications to exercise testing
 - 11) Inability to sit and pedal unassisted, at a cadence of at least 55 rpm during unloaded warm up, in a cycle ergometry chair and complete a maximal Cardio Pulmonary Exercise Test (CPET)
 - 12) Inability to sit and pedal unassisted in a recumbent tricycle
 - 13) For individuals completing the MRI: Any contraindication to MRI Including:
 - ANY intra-luminal implant, filter, stent or valve replacement
 - ANY type of life assist device, pump, or prosthetic
 - ANY vascular clip or clamp
 - ANY surgically placed clips or clamps or bands on visceral organs
 - ANY intracranial implants of any type other than dental fillings
 - ANY non-removable piercings, jewelry, or medicinal patch
-

	
 – ANY personal history of intraocular injury or fragment in or around the orbit that cannot be cleared through radiologic examination. – ANY personal history of bullet, shrapnel, or stabbing wounds that cannot be cleared through radiologic evaluation. – Inability to lie flat in the MRI scanner for 60-90 minutes. * participants who cannot complete the MRI will not be excluded from participation in the remainder of the study procedures if they meet those inclusion and exclusion criteria 
 14) Use of any investigational agent within 4 weeks of enrollment, except open-label extension phase 15) Females: Pregnant, lactating, or planning to become pregnant during their participation. 16) Any medical condition, in the opinion of the investigator that will interfere with the safe completion of the study. 17) Parents/guardians or participants who, in the opinion of the Investigator, may be non-compliant with study schedules or procedures.
Number Of Subjects	We anticipate enrolling 80 participants (~40% pediatric, ~60% adult) in order to obtain complete data on 64 participants. Pediatric participants (n = 32) will complete study procedures at The Children's Hospital of Philadelphia. Adult participants (n = 48) will complete study procedures at The Children's Hospital of Philadelphia and The Hospital of the University of Pennsylvania.
Study Duration	Each individual's participation will last up to 36 weeks (+/- 1 Week).
Study Phases Screening Intervention Follow-Up	(1) Screening: Participants will undergo a telephone screening to assess eligibility and then, within ~12 weeks, complete an in-person baseline visit to confirm eligibility. (2) Baseline Visit: Participants confirmed to be eligible after completion of screening procedures will be assigned to 1 of 4 arms and begin the 12-week intervention. (3) Follow-Up: Participants will return after the 12-week intervention to complete follow-up procedures.
Outcomes	VO ₂ max (primary outcome); S _i (key secondary outcome); muscle mass (key secondary outcome); muscle mitochondrial OXPHOS capacity via CrCEST MRI (key secondary outcome); NAD ⁺ from

	muscle biopsy (key secondary outcome); nutrient-specific mitochondrial OXPHOS capacity from muscle biopsy (key secondary outcome)
Safety Evaluations	Safety will be monitored through the collection of laboratory assessments at baseline, interim, and follow-up. Participants will also be monitored using a standardized assessment of symptoms. We will use the Common Terminology Criteria for Adverse Events (CTCAE, version 5.0, U.S. Department of Health and Human Services) to grade adverse events. Individuals who experience a new Grade 3 or higher AE may need to stop study participation at the discretion of the investigative team.
Statistical And Analytic Plan	Linear mixed-effects modeling will be used to evaluate effect of interventions over time on the primary and key secondary outcomes. The models incorporate subject-specific random effects to account for within-subject correlation due to repeated measures. Group averages, as well as subject-specific intercepts and slopes, will be estimated to capture potential variations in the baseline values and slopes among individuals. Linear mixed-effects models accommodate missing data due to dropout, such that all randomized participants can be included. We will compare participants who complete the study with those who do not, and identify potential factors that are associated with dropout. In the mixed-effects models, we will adjust for time-invariant covariates (age at randomization, sex) and time-varying covariates (lean mass, muscle OXPHOS capacity, muscle NAD ⁺ content). By including these indices of “muscle quality” as covariates in the models, we will be able to assess whether intervention effects are explained by these effects. To assess other potential factors influencing outcomes, we will also analyze the incremental effect of adding each of the other measured covariates (final dose of NR achieved, final training intensity achieved, FA severity) to the models.
DATA AND SAFETY MONITORING PLAN	The PI will designate an independent Data Safety Monitoring Board (DSMB) to perform an independent review of ongoing study progress and safety. The DSMB will likely consist of a cardiologist, neurologist, and endocrinologist with expertise in FA, and also a statistician. The cardiologist will serve as chair, and will facilitate meetings as per the DSMB charter.

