1.3.2 Outcome Analysis

The primary outcome for **Aim 1** is the change in peak VO₂ from baseline to 12 weeks.

Rationale for selection of the primary outcome:

- CPET measures are widely used, objective, and highly associated with health.⁷⁹
- Peak VO₂ demonstrates excellent reproducibility and reflects disease progression in FA.⁸⁰
- As our preliminary data show, peak VO₂ contributes to both exercise capacity and daily function.⁸¹

Key secondary outcomes (change from baseline to 12 wks):

Primary analysis: We will fit a linear model with the outcome of change in peak VO₂ and covariates of treatment arm, baseline peak VO₂, and randomization stratum (child vs. adult). In a modification of previous strategies for the analysis of factorial designs⁸², the family-wise Type I error rate is maintained at <5% by using a two-stage approach: a Holm-Bonferroni correction is applied in Stage 1, and a single contrast is pre-specified in Stage 2 (**Table 3**). In Stage 1, we test if mean peak VO₂ in any of the active treatment arms differs from control (no-exercise + placebo). In Stage 2, if the exercise+NR arm differs from the control arm, we then compare

exercise+NR to exercise alone (exercise + placebo), to determine whether NR increases mean peak VO₂ beyond the effect of exercise alone (exercise + placebo).

Secondary analyses: The primary analysis will be repeated with each secondary outcome. Additional models will explore whether change from baseline can be explained by either baseline demographic or clinical covariates (age at randomization, sex, FRDA disease activity – mFARS upright stability score), baseline characteristics of muscle quality (appendicular lean mass – lower extremity, muscle OXPHOS capacity – CrCEST recovery time constant, NAD⁺ content of blood or muscle), or features of the intervention in the relevant intervention groups only (final dose of NR, final training intensity in Mets per week). **Sex as a biological variable:** We will include sex as a covariate. We will report the results of sex-stratified analyses for the entire cohort and describe age/puberty effects for children.

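### The protocol synopsis and the SAP define different analyses of the primary outcome, and the synopsis model adjusts for post-randomisation muscle variables

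*Protocol*

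**What the plan says.** **Protocol synopsis, Statistical And Analytic Plan.** "Linear mixed-effects modeling will be used to evaluate effect of interventions over time on the primary and key secondary outcomes". In those models "we will adjust for time-invariant covariates (age at randomization, sex) and time-varying covariates (lean mass, muscle OXPHOS capacity", followed by muscle NAD+ content. The reason given is that, with these muscle indices in the model, "we will be able to assess whether intervention effects are explained by these effects". The section also says that "subject-specific intercepts and slopes, will be estimated", and that because mixed models cope with dropout, everyone randomised can be kept in the analysis. It describes no model without the muscle variables. Only a further set (final NR dose, final training intensity, FA severity) is described as being added incrementally.

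**Protocol synopsis, other sections.** The Study Rationale says that exercise and NAD+ precursors "may each produce increases in OXPHOS that translate into increased" VO2max. Outcomes lists "muscle mitochondrial OXPHOS capacity via CrCEST MRI (key secondary outcome"), and gives muscle mass and muscle NAD+ the same status. The note to exclusion criterion 13 says that "participants who cannot complete the MRI will not be excluded from participation in the remainder of the study procedures", provided they meet the other criteria.

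**SAP section 1.3.2, Primary analysis.** "We will fit a linear model with the outcome of change in peak" VO2, with arm, baseline peak VO2 and the child/adult stratum as covariates. Muscle-quality variables enter only at their baseline values, in additional exploratory models. Section 1.1 defines the primary endpoint without adjustment for lean mass and makes the lean-mass version secondary.

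**The concern.** The primary objective is the effect of NR plus exercise on VO2max. A model that conditions on 12-week lean mass, OXPHOS and NAD+ answers another question: how much effect remains once changes in those variables are held fixed. If the treatments work as the rationale proposes, part of the benefit passes through those variables and is removed from the arm coefficient.

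Two further problems come with the synopsis model. A mixed model tolerates missing outcomes but not missing covariates, so a visit without an MRI value is lost unless it is imputed. And a subject-specific slope is requested although the outcome is analysed at only two times.

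The two documents also disagree on model class, form of outcome and covariates. A trial should have one pre-specified primary analysis, and a reader of the protocol would expect a different one from a reader of the SAP.

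**Working it through.** **1. The two models side by side**

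| | Protocol synopsis | SAP 1.3.2 |
|---|---|---|
| Model | Linear mixed model | Linear model |
| Outcome | Repeated measurements over time | Change, baseline to 12 weeks |
| Baseline covariates | Age, sex | Baseline peak VO2, child/adult stratum |
| Post-randomisation covariates | Lean mass, muscle OXPHOS, muscle NAD+ | None |

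They differ in every row. The synopsis applies its model to the key secondary outcomes as well. Read literally, muscle mass, OXPHOS and NAD+ would then be adjusted for themselves or for one another.

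**2. The plan's own power figure**

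SAP Table 3, Scenario 3, Stage 2 compares 5.5 with 2.9 mL/kg/min, a difference of 2.6, with SD of change 2.5 and 16 per arm. The standard error is 2.5 × √(2/16) = 0.884 and the noncentrality is 2.6/0.884 = 2.94. A two-sided t-test at 0.05 with 30 df gives power 81.2%, against 81% stated. The figure reproduces. (The text of section 1.4 uses SD 3, which gives 66% at alpha 0.05. That is a separate matter; the table's SD is used here.)

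**3. Illustration of attenuation**

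The mediated share is not in the documents, so a range is assumed. The adjusted difference is 2.6 × (1 − share), with SD held at 2.5 and 16 per arm.

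| Share mediated (assumed) | Adjusted difference | Noncentrality | Power |
|---|---|---|---|
| 0% | 2.60 | 2.94 | 81% |
| 25% | 1.95 | 2.21 | 57% |
| 50% | 1.30 | 1.47 | 30% |
| 75% | 0.65 | 0.74 | 11% |

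Holding SD at 2.5 ignores any residual variance that the covariate explains. A simulation (4,000 runs) let the mediator explain 20% of the variance of change, also assumed. With complete data the adjusted estimates were 1.97, 1.29 and 0.68 and power was 61%, 28% and 9% at 25%, 50% and 75% mediated. The unadjusted model stayed near 2.6 and 81%. With no mediation, adjustment raised power to 88%.

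**4. Missing covariates**

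The number without MRI is not stated. If a quarter of 16 per arm lacked a covariate (assumed), 12 remain. The standard error is 2.5 × √(2/12) = 1.021, the noncentrality 2.6/1.021 = 2.55 and power 68% with no mediation at all. Someone with no scan at either visit leaves the model entirely. Someone missing only the 12-week scan keeps a baseline row but gives no adjusted information on change.

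**5. Random slope**

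Two measurements per person supply three second moments: two variances and one covariance. A random intercept, a random slope, their covariance and a residual variance make four parameters. The slope cannot be separated from the residual without a restriction that the synopsis does not state. The interim assessment in the synopsis is for safety laboratories, so it adds no third outcome time.

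**The case against.** The strongest reply is that the synopsis states a purpose for the muscle covariates, namely to see whether effects are explained by muscle quality, and never labels the adjusted coefficient as the primary estimate. The only text headed as a primary analysis is in the SAP, and that model is sound. The SAP appears to be the later document, since it discusses a 2022 licence, and it adds multiple imputation as a sensitivity analysis. The available protocol text is a synopsis, and the SAP refers to a protocol table not shown there, so a fuller protocol section may contain an unadjusted model or a rule on which document governs.

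Much of this stands. A reader might infer that the trial's primary result will be biased toward zero. The documents do not support that: the SAP's primary model contains none of these covariates, and attenuation under the synopsis model depends on real mediation, whose size is not given. Conditioning on a mediator that shares causes with the outcome could also bias in either direction. Nor do the documents support treating biopsy as optional; only the MRI is documented as something a participant may go without. Because the meaning of complete data is not defined, taking a further loss off 16 per arm may count some participants twice. The random slope is a fitting problem and does not in itself bias the arm comparison.

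The stated purpose does not remove the conflict. Asking whether an effect is explained by a mediator requires the unadjusted effect for comparison, and the synopsis specifies neither that model nor a secondary label for the adjusted one.

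**Conclusion.** The point holds as a conflict between documents and a defect in the synopsis model, not as a flaw in the SAP's primary analysis. As written, the synopsis model would estimate a direct effect, would drop visits without MRI data despite the assurance that everyone randomised can be included, and asks for a random slope that two outcome times cannot identify.

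The figures are conditional. Stage 2 power of 57% or 30% assumes 25% or 50% mediation, SD 2.5 and 16 per arm; 68% assumes no mediation and a quarter of participants lacking a covariate. If nothing is mediated and the covariates are complete, adjustment costs nothing and may gain power. The conflict itself rests on no assumption beyond the available text.

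**What to change.** Amend the protocol's statistical section to the SAP primary model: change in peak VO2 on arm, baseline peak VO2 and child/adult stratum. State that the SAP governs the analysis. Keep time-varying lean mass, OXPHOS and NAD+ only in an exploratory analysis labelled as mediation. Report it beside the unadjusted effect, and say how missing MRI or biopsy values are handled. Baseline values may stay as covariates in additional models, as the SAP already has them. Delete the random slope.

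The cost is a wording amendment. The SAP model already exists, and sample size, visits and data collection are unchanged.

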1.1 Primary Endpoint

The primary outcome for **Aim 1** will be:

- within-participant change in peak VO_2 , the highest oxygen uptake achieved on adaptive cardiopulmonary exercise testing, with peak VO_2 expressed in L/min (unadjusted for individual lean mass)

Peak VO_2 refers to the highest oxygen uptake achieved during specific exercise testing conditions (versus $\text{VO}_{2\text{max}}$, which is the theoretical maximal oxygen uptake achievable by the individual, typically confirmed by demonstrating a plateau in VO_2 during while work continues to increase, along with a combination of other factors, PMID: 39873542). Not all individuals who perform maximal test according to our criteria will demonstrate this plateau. In this ramp, symptom limited test, participants continued until maximal volition or until limiting symptoms occurred (PMID: 38515223). Ratio methods for scaling VO_2 to size will produce lower values in those with higher body weight or body fat, as reviewed in PMID: 39873542.

Key Secondary endpoints for Aim 1 include within-participant changes in:

- within-participant change in peak VO_2 , the highest oxygen uptake achieved on adaptive cardiopulmonary exercise testing, with peak VO_2 expressed in mL/min, accounting for individual lean mass (appendicular, lower extremity only), the latter of which is a key driver of peak VO_2
- max workload in Watts, with and without accounting for individual lean mass (appendicular, lower extremity only),
- max O_2 pulse in ml/beat,
- AT in ml/min, with and without accounting for individual lean mass (appendicular, lower extremity only),
- muscle strength (dynamometry in N), with and without accounting for individual lean mass (appendicular, lower extremity only)
- fatigue (Fatigue Impact Scale⁵⁷),
- physical activity (PADS-R⁵⁸),
- resting heart rate,
- FA-HI (PMID: 37646046),
- heart rate variability via MCOT

1.2 Secondary Endpoints

The primary outcome for **Aim 2** will be

- within-participant change in whole body insulin sensitivity (WBIS_I), reflecting mostly the contribution from skeletal muscle.

Other key secondary outcomes include within participant changes in:

- whole body insulin sensitivity S_i ⁷⁶,
- fasting glucose,
- fasting insulin,
- fasting lactate,
- glucose area under the curve (AUC),
- insulin AUC,
- first- and second-phase insulin secretion estimates from OGTT⁷⁸,
- disposition index,
- insulin clearance,
- lactate AUC,
- whole-body lactate clearance (K_{01})⁷⁷

1.3 Statistical Methods

1.3.1 Baseline Data

Baseline and demographic characteristics will be summarized by standard descriptive statistics (i.e., means and standard deviations or medians and interquartile ranges for continuous variables such as age, percentages for categorical variables such as gender) and graphically.

1.3.2 Outcome Analysis

The primary outcome for **Aim 1** is the change in peak VO₂ from baseline to 12 weeks.

Rationale for selection of the primary outcome:

- CPET measures are widely used, objective, and highly associated with health.⁷⁹
- Peak VO₂ demonstrates excellent reproducibility and reflects disease progression in FA.⁸⁰
- As our preliminary data show, peak VO₂ contributes to both exercise capacity and daily function.⁸¹

Key secondary outcomes (change from baseline to 12 wks):

Primary analysis: We will fit a linear model with the outcome of change in peak VO₂ and covariates of treatment arm, baseline peak VO₂, and randomization stratum (child vs. adult). In a modification of previous strategies for the analysis of factorial designs⁸², the family-wise Type I error rate is maintained at <5% by using a two-stage approach: a Holm-Bonferroni correction is applied in Stage 1, and a single contrast is pre-specified in Stage 2 (**Table 3**). In Stage 1, we test if mean peak VO₂ in any of the active treatment arms differs from control (no-exercise + placebo). In Stage 2, if the exercise+NR arm differs from the control arm, we then compare

exercise+NR to exercise alone (exercise + placebo), to determine whether NR increases mean peak VO₂ beyond the effect of exercise alone (exercise + placebo).

Secondary analyses: The primary analysis will be repeated with each secondary outcome. Additional models will explore whether change from baseline can be explained by either baseline demographic or clinical covariates (age at randomization, sex, FRDA disease activity – mFARS upright stability score), baseline characteristics of muscle quality (appendicular lean mass – lower extremity, muscle OXPHOS capacity – CrCEST recovery time constant, NAD⁺ content of blood or muscle), or features of the intervention in the relevant intervention groups only (final dose of NR, final training intensity in Mets per week). **Sex as a biological variable:** We will include sex as a covariate. We will report the results of sex-stratified analyses for the entire cohort and describe age/puberty effects for children.

Omaveloxolone (OMAV) was licensed in 2022 in the U.S. for the treatment of FRDA in individuals at least 16 years of age. “OMAV” is expected to be used eventually by most patients with FRDA for whom it is approved. In this study, a small fraction of participants are expected to be prescribed OMAV because of when the study was started (first participant enrolled in 2020, when OMAV was not yet approved) and its age range (including individuals under age 16 years, for whom OMAV is not yet approved). We will adjust for OMAV prescription as a pre-specified secondary analysis.

The main outcome for **Aim 2** is change in S_i⁷⁶ (reflecting mostly muscle) from baseline to 12 weeks. Rationale for selection:

Key secondary outcomes (change from baseline to 12 wks): fasting glucose, insulin, lactate; glucose, insulin, GLP1, lactate AUC; insulin secretion estimates from OGTT⁷⁸; insulin clearance; FFA flux; CGM time spent with blood glucose above 140 mg/dL, CGM glucose coefficient of variation

Analysis of primary outcome and key secondary: The same two-stage approach as outlined in **Aim 1** will be used to analyze **Aim 2** outcomes (See **Table 4** from the protocol below). To assess how aerobic capacity is associated with glycemic outcomes, we will also describe the incremental effect of adding peak VO₂ as a covariate to statistical models. **Sex as a biological variable** will be addressed as in Secondary analyses above and as a subgroup (see below).

Missing Data

We will explore document rates of missing data and explore differences between the baseline covariates of individuals with and without missing data, both overall and by treatment arm. Using multiple imputation, we will carry out a sensitivity analysis for the primary and secondary analyses, exploring the impact of the missingness under the missing at random assumption.

Safety Analysis

All participants enrolled in the study who receive the supplement/placebo will be included in the safety analysis. The frequencies of AEs by type and severity will be summarized by arm and the relationship to the supplement/placebo and to exercise will be summarized by grouping across arms. 'Falls' are pre-specified as a particular AE of interest. SAEs (if any) will be described in detail.

Subgroup Analyses

The four pre-specified subgroups are: Age (child vs. adult, stratified at age 18 years), omaveloxolone (OMAV) status (prescribed or not), biological sex (male vs. female) and Respiratory Exchange Ratio (RER) achieved during CPET (greater than/equal to vs. less than 1). For the primary outcome, the analysis will include an hypothesis test of the interaction between the subgroups and study arm. These analyses will be unadjusted for multiple comparisons. A forest plot including two-sided 95% CI will be created.

Using a linear model, the association of duration of OMAV prescription with outcome will be explored among individuals who are prescribed the drug.

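### The omaveloxolone (OMAV) subgroup test covers ages 10 to 40 although approval starts at 16, so part of any age difference in arm effect can appear as an OMAV-by-arm interaction

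*SAP*

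**What the plan says.** The Protocol synopsis admits "Males and Females, Age 10 to 40 years (inclusive". SAP section 1.3.2 records that OMAV was "licensed in 2022 in the U.S. for the treatment of FRDA in individuals at least 16 years of age". It gives two reasons why few participants will have it. One is calendar time: "a small fraction of participants are expected to be prescribed OMAV because of when the study was started". Enrolment opened in 2020, ahead of the 2022 approval. The other is the age range: "including individuals under age 16 years, for whom OMAV is not yet approved".

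Under Subgroup Analyses the same section names four pre-specified subgroups, among them "omaveloxolone (OMAV) status (prescribed or not), biological sex (male vs. female". For the primary outcome, "the analysis will include an hypothesis test of the interaction between the subgroups and study arm". A forest plot follows, with no multiplicity adjustment. Nothing limits the OMAV comparison to participants aged 16 or over, or to those enrolled after approval. Age is a separate subgroup, cut at 18. In the primary model, age enters only through the child/adult randomization stratum, as a main effect.

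On duration of use, the SAP says only that, with a linear model, "the association of duration of OMAV prescription with outcome will be explored among individuals who are prescribed the drug". It lists no covariates.

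**The concern.** The SAP names age as a driver of OMAV status but does not carry that into the subgroup definition. If prescribing follows the approval, the prescribed group is aged 16 to 40, while the not-prescribed group holds every 10- to 15-year-old as well as older non-users. The OMAV-by-arm contrast is then partly a contrast between older and younger participants. A child/adult main effect allows the two age groups to have different mean changes. It does not allow the effect of an arm to differ between them, so it cannot keep such a difference out of the OMAV-by-arm term.

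At stake is the reading of one forest-plot row. OMAV is expected to become common treatment in this disease, so readers will look at that row. A shift produced by age could be taken as evidence that OMAV strengthens or weakens the response to NR plus exercise.

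**Working it through.** **Inputs from the documents**
- About 40% pediatric (32 of 80) and 64 with complete data: Protocol synopsis, Number Of Subjects.
- OMAV approved from 16, few users expected, no number given: SAP 1.3.2.
- SD of the 12-week change 2.5 mL/kg/min: Table 3 footnote. 16 per group: SAP 1.4.

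**Assumptions**
- Pediatric ages spread evenly over 10 to 17, and nobody under 16 prescribed OMAV.
- About 10 users among 64.
- The under-16 arm effect is a fraction *r* of the older effect, with *r* from 0.5 to 0.8.
- No true OMAV interaction.

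**1. Anchor.** The SAP gives no figure for the OMAV test. As a check on SD and group size, Table 3 Scenario 3, Stage 2 (5.5 vs 2.9, difference 2.6, SD 2.5, 16 per group, two-sided 0.05) gives 81.2% power by the t-test, against 81% stated. It reproduces.

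**2. Share under 16 among the not-prescribed.** Under-16s: 64 × 0.40 × 6/8 = 19.2, about 19. Not prescribed: 64 − 10 = 54. Share *s* = 19/54 = 0.35, against 0 among the prescribed. With 20–40% of participants under 16 and 10–25% prescribed, *s* runs from 0.20/0.90 = 0.22 to 0.40/0.75 = 0.53. The top end needs every pediatric participant to be under 16 and a quarter of the trial to be on OMAV.

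**3. Spurious interaction.** Let *E* be the older effect. The prescribed group shows *E*; the not-prescribed group shows (1 − *s*)*E* + *s r E*. The difference is *s*(1 − *r*)*E*.
- *r* = 0.8: 0.35 × 0.2 = 7% of *E*.
- *r* = 0.5: 0.35 × 0.5 = 18% of *E*.
- *r* = 1: zero.

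**4. Is *r* below 1 plausible?** The documents give no age-specific effect, but SAP 1.1 sets the primary endpoint in L/min, unscaled for lean mass. Suppose everyone gains 2.6 mL/kg/min. At assumed weights of 35 and 65 kg the gains are 0.091 and 0.169 L/min, a ratio of 0.54; at 50 and 65 kg the ratio is 0.130/0.169 = 0.77. An equal response per kilogram can therefore still be unequal on the endpoint's scale.

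**5. Simulation of the planned model** (arm, child/adult stratum, OMAV, OMAV-by-arm; SD 2.5; 30% under 16; baseline peak VO2 omitted). A deliberately large age difference of 2.6 mL/kg/min was placed in the NR + exercise arm, with the under-16s gaining more, so the sign is negative here.

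| Analysis | Mean false contrast, N = 64, 15% prescribed |
|---|---|
| All ages, as planned | −0.97 |
| Age 16 and over only | −0.02 |
| All ages plus under-16-by-arm terms | 0.09 |

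At N = 6,400 the planned analysis gives −0.91, against the formula's 0.353 × 2.6 = 0.92, with the stratum main effect in the model. At N = 64 the contrast has a sampling SD of about 2.7 (15% prescribed) or 2.3 (25%), and the 3-df test rejects in 5.3% or 6.7% of simulated trials, against 5% nominal. With 15% prescribed, about a quarter of trials had an empty arm-by-OMAV cell, so the full interaction could not be estimated.

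**6. Duration model.** If arm were left out, residual SD = √(2.5² + variance of the four arm means).
- Scenario 1: √(6.25 + 1.80) = 2.84
- Scenario 2: √(6.25 + 2.56) = 2.97
- Scenario 3: √(6.25 + 3.79) = 3.17
- Scenario 4: √(6.25 + 1.69) = 2.82

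These are in mL/kg/min, as in Table 3; the primary endpoint is in L/min.

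**The case against.** The strongest reply is that the bias depends on an age difference in arm effect that the documents do not quantify, and that even a large one is swamped by noise: about 1 mL/kg/min against a sampling SD of 2.3 to 2.7. OMAV status is not randomized, the SAP makes no causal claim about it, and correlated subgroup factors are an ordinary limit of such analyses. The age subgroup appears in the same forest plot, and section 1.3.2 also plans models with age at randomization and a description of age and puberty effects. Much of this stands. It limits the weight of the point but does not remove it: the age subgroup is a separate test with its cut at 18, so it can help interpretation without correcting the OMAV row.

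Two further replies also stand. Restricting by age leaves pre-approval enrolees aged 16 or over among the not-prescribed, so calendar time stays mixed in. And with so few users, sparse cells may limit the test more than age does.

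Some stronger readings are tempting, but the documents do not support them:
- *The whole age difference becomes an OMAV interaction.* Only the share *s* of it does, about 35% with 10 users.
- *Under-16s contribute nothing but confounding.* They also help to estimate the residual variance and the baseline peak VO2 slope.
- *The distortion reaches 28%.* That takes 30 users of 64 (19/34 = 56%, × 0.5), which does not fit the small fraction the SAP expects.
- *The duration model excludes arm.* The SAP lists no covariates; silence is not exclusion.

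**Conclusion.** The point holds as a minor one. As defined, the OMAV subgroup test lets part of any age difference in arm effect pass as an OMAV-by-arm interaction, and the child/adult main effect does not prevent it. The size is about 7% to 18% of the older group's effect, given 64 completers, 19 under 16, about 10 users, no use under 16, and an under-16 effect of 0.5 to 0.8 of the older one. Without an age difference in effect there is no bias, and off-label use under 16 would reduce it. The primary analysis does not involve OMAV status and is unaffected. A reader might infer that the trial is likely to announce a false OMAV interaction; the simulated rejection rates of 5.3% to 6.7% do not support that. The duration model is underspecified, which is a secondary matter.

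**What to change.** - Restrict the OMAV subgroup test and its forest-plot rows to participants aged 16 or over at randomization.
- State that the result is exploratory and still mixed with calendar time, because enrolment began before the 2022 approval; or add a sensitivity analysis limited to participants enrolled after approval.
- Specify the OMAV-duration model: include treatment arm, and baseline peak VO2 and age if numbers allow. Arm is the priority, since omitting it would raise the residual SD from 2.5 to about 2.8–3.2 mL/kg/min across the Table 3 scenarios.

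Adding age-by-arm terms to the all-ages model also removes the bias, but it adds parameters to a sparse model, so restriction is simpler.

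The cost is SAP wording, fewer not-prescribed participants (54 − 19 = 35 under the assumptions above) and a slightly larger standard error. With 10 users spread evenly over four arms, the ratio of standard errors is √[(1/2.5 + 1/8.75)/(1/2.5 + 1/13.5)] = 1.04, so about 4%. The simulations gave 5% to 8% (for example 2.45 against 2.30 with 25% prescribed). The loss is small because the few users dominate the variance.
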